#### **4.1.7.3. Post-Infusion**

Participants will report to either the vector-administration center or follow-up center for safety evaluations, according to the protocol assessments (See the Schedule of Activities for further details regarding each visit), for up to 52 ( $\pm 2$ ) weeks after infusion of PF-06838435. During the safety observation period, in-home service provider can be utilized, if needed, for mobile-phlebotomy and sample-collection services during the visits which do not require a physical examination.

#### **4.2. Scientific Rationale for Study Design**

This study will investigate up to three PF-06838435 dose levels ( $5 \times 10^{11}$ ,  $1 \times 10^{12}$ , and  $2 \times 10^{12}$  vg/kg). Safety of these dose levels is supported by previous human clinical trials of AAV2 and AAV8 vectors encoding hFIX, as well as the NHP studies with AAV-Spark100-hFIX19-Padua and with SPK-9001, in which dose levels up to  $5 \times 10^{12}$  vg/kg were infused without evidence of adverse effects.

Dose escalation and dose level expansion strategies are employed in the study based on vector-derived FIX activity levels as well as any immune responses against AAV capsid.

The primary study objective is the assessment of safety and tolerability of a single IV infusion of PF-06838435. This study also aims to characterize kinetics of PF-06838435. The vector-derived endogenous (not affected by intercurrent FIX product infusions) FIX:C activity levels will be characterized by post-treatment population mean. The assessment will be done for each dose of PF-06838435.

As no formal hypotheses will be tested in this study, the sample size is based on the need to establish the initial safety and kinetic profile of PF-06838435. Up to 20 evaluable participants will be dosed in the study ([Section 9.3](#)).

#### **4.3. Justification for Dose**

Non-clinical pharmacology, toxicology, and biodistribution studies of AAV-Spark100-hFIX19-Padua have been performed in three animal models (wild-type [WT] mice, HB mice, and NHPs) to evaluate expression and safety. PF-06838435 has also been infused into NHP and demonstrated to drive expression of FIX at levels equivalent to AAV-Spark100-hFIX19-Padua. Long-term safety and immunogenicity of the FIX-Padua protein were evaluated in a hemophilic canine model using an AAV8-FIX-Padua vector. These data are relevant to PF-06838435 since FIX gene delivery using AAV-Spark100 results in similar levels of expression as compared to gene delivery using AAV8 in these species. Based on the Sponsor's experience, studies in mice have not been predictive of FIX expression levels in humans, but studies in dogs and NHPs have correlated well with levels in human participants. The non-clinical studies in NHP using AAV Spark100-hFIX19-Padua infused at a dose of  $1 \times 10^{12}$  vg/kg resulted in steady-state vector-derived FIX activity levels of  $\sim 27\%$  (range 22.7-30.7%).

A dose of  $5 \times 10^{12}$  vg/kg was administered without evidence of adverse effects in NHPs. It is widely accepted that maintaining factor activity levels above 1-2% of normal may prevent bleeding and ultimately arthropathy in patients with severe hemophilia. Based on large

animal models of the disease and prior clinical experience with AAV8-hFIX19, the starting dose of  $5 \times 10^{11}$  vg/kg may result in detectable circulating vector-derived factor IX (FIX:C) activity levels above background levels. This starting clinical dose ( $5 \times 10^{11}$  vg/kg) is ~10 fold lower than the highest dose studied in the Good Laboratory Practice (GLP) toxicology study. Furthermore, non-clinical safety data demonstrate that doses of  $1 \times 10^{12}$  vg/kg,  $2 \times 10^{12}$  vg/kg and  $5 \times 10^{12}$  vg/kg are generally well tolerated in NHPs and support the proposed up to three dose levels of  $5 \times 10^{11}$ ,  $1 \times 10^{12}$ , and  $2 \times 10^{12}$  vg/kg to be investigated in this study.

It is worth noting that the preliminary data of an ongoing Baxter trial (NCT#01687608) using self-complementary AAV8-hFIX-Padua (BAX-335), presented at the 8th Annual Congress of the EAHAD on 12th February 2015 in Helsinki, Finland, showed vector-derived FIX:C activity levels of ranging from <1 – 60% at doses of  $2 \times 10^{11}$  vg/kg,  $1 \times 10^{12}$  vg/kg and  $3 \times 10^{12}$  vg/kg with no safety concerns. One common aspect of our previous trial (IND 9398) and Baxter's study is that vector preparations with minimal empty capsid content were used. The outcome of both trials in the low dose levels was disappointing, showing sub-therapeutic or no FIX expression in most of the participants. Specifically, three out of three participants treated with  $4 \times 10^{11}$  vg/kg of AAV2-hFIX16 and one out of two participants treated with  $2 \times 10^{11}$  vg/kg of BAX-335 manifested no detectable factor IX expression. Activity levels from the second participant dosed with BAX-335 could only be detected due to the hyperactivity of the Padua variant as antigen levels may not have been higher than 0.25 - 0.5% of normal.

Meanwhile, both participants infused with  $2 \times 10^{11}$  vg/kg of scAAV2/8-LP-hFIXco with an empty:full capsid ratio of approximately 5:1 in the SJ-UCL hemophilia B trial expressed FIX above background levels. Thus, the Sponsor hypothesizes the presence of an excess of empty capsids may absorb low-level NAbs and non-NAbs, permitting liver transduction after peripheral vector infusion even at low doses. PF-06838435 will contain a mixture of empty and full capsid particles (cp), at a ratio comparable to the ratio used in the SJ-UCL study.

Additional information for the C0371005 Phase 1/Phase 2a study results may be found in the Investigator's Brochure (IB).

#### 4.3.1. Study Stopping Rules

Pfizer may terminate this study at any time after informing the Investigators. Pfizer, or designee, will notify the Investigator(s) and appropriate regulatory authorities if the study is

---

suspended, terminated or completed. If the study is suspended or terminated, the following instructions should be followed, unless the DMC and/or the Study Medical Monitor advise otherwise:

1. Participants who have already received PF-06838435 will continue to maintain the protocol schedule of activities;
2. Participants who have already enrolled into the study but have not received PF-06838435 will wait for DMC recommendation. The scheduled date for PF-06838435 infusion may be postponed or cancelled.

The occurrence of any of the following medically important events will result in suspension of further enrollment while the events are under investigation:

- Any drug-related death during the study;
- Any participant develops drug-related or possibly drug-related Grade III-IV toxicity such as FIX inhibitor, allergic reaction (bronchospasm and anaphylaxis), excluding elevated transaminases;
- Any participant develops drug-related or possibly drug-related Grade III-IV elevated transaminases that fails to improve or resolve within four weeks on the immunosuppressive regimens;
- Any participant develops drug-related or possibly drug-related Grade IV (>10-fold) elevated transaminases;
- Any participant reaches >150% of normal vector-derived FIX:C activity levels and develops drug-related or possibly drug-related thrombotic event after vector infusion (with the exception of IV infusion-site thrombophlebitis) or if any participant develops a sustained (defined as > 6 weeks) FIX activity levels of >150%;
- Participant experience a medically important event that warrants further evaluation;
- Any occurrence of a malignancy at any point after vector infusion that is possibly, probably, or definitely related to the investigational product.

It is important to note that AAV vector-mediated insertional mutagenesis, if it should occur, is not likely to be observed in the first year after gene transfer; therefore, Pfizer intends to provide long-term safety monitoring of participants in the extension study.

In addition to halting enrollment, such an event will be handled as a serious adverse event (SAE) and reported in the time frame according to [Section 8.3.1.1](#) (Reporting of SAEs to Pfizer) of the protocol. The DMC will review data relevant to the event and will receive input from Pfizer and/or Investigator before providing appropriate recommendations. The event and the DMC's recommendation will be discussed with the U.S. Food and Drug Administration (FDA) and other regulatory authorities prior to re-initiation of enrollment.

All participants who were infused with the investigational product will continue to comply with the follow-up schedule according to the protocol.

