Not related	An event that does not follow a reasonable temporal sequence from administration of investigational product AND that is likely to have been produced independently by the subject’s clinical state, environmental or toxic factors, or other modes of therapy administered to the subject.

Unlikely	Any event that does not follow a reasonable temporal sequence from administration of investigational product OR that is likely to have been produced by the subject's clinical state, environmental or toxic factors, or other modes of therapy administered to the subject.
Possibly	Any reaction that follows a reasonable temporal sequence from administration of investigational product OR that follows a known response pattern to the suspected drug AND that could not be reasonably explained by the known characteristics of the subject's clinical state, toxic or environmental factors or other modes of therapy administered to the subject.
Related	Any reaction that follows a reasonable temporal sequence from administration of investigational product AND that follows a known response pattern to the suspected drug AND that recurs with re-challenge, AND/OR is improved by stopping the drug or reducing the dose.

Follow-up of AEs and SAEs

 
• The investigator is obligated to perform or arrange for the conduct of supplemental measurements and/or evaluations as medically indicated or as requested by Pfizer to elucidate the nature and/or causality of the AE or SAE as fully as possible. This may include additional laboratory tests or investigations, histopathological examinations, or consultation with other health care professionals.
 
• If a participant dies during participation in the study or during a recognized follow-up period, the investigator will provide Pfizer Safety with a copy of any post-mortem findings including histopathology.
 
• New or updated information will be recorded in the originally completed CRF.
 
• The investigator will submit any updated SAE data to Pfizer Safety within 24 hours of receipt of the information.
 

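### In Protocol 4.3.1, death is the only one of six causality-conditioned suspension triggers that does not expressly cover possibly related events; the practical gap is small and closes with three words

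*Protocol*

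**What the plan says.** Protocol Section 4.3.1 (Study Stopping Rules) introduces a list of seven bullets, any of which "will result in suspension of further enrollment while the events are under investigation". The bullet for death is "Any drug-related death during the study". Its neighbours are worded more broadly. For example, one reads "Any participant develops drug-related or possibly drug-related Grade IV (>10-fold) elevated transaminases", and the malignancy bullet covers a malignancy "that is possibly, probably, or definitely related to the investigational product". One bullet carries no causality condition at all: "Participant experience a medically important event that warrants further evaluation".

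A trigger brings more than a pause. The same section says "The DMC will review data relevant to the event", and requires the event and the DMC's recommendation to be discussed with FDA and "other regulatory authorities prior to re-initiation of enrollment".

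Protocol Section 10.3.3 gives four causality categories: Not related, Unlikely, Possibly and Related. Possibly and Related are separate. Related needs a plausible time sequence and a known response pattern. It also needs an event "that recurs with re-challenge" and/or one that improves when the drug is stopped or reduced.

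**The concern.** Four bullets in the list add possibly drug-related to drug-related, and the malignancy bullet begins its range at possibly. A site reading the list in order could reasonably conclude that the omission for death is deliberate, because otherwise the extra words elsewhere do no work. That would give the gravest event a narrower express trigger than a laboratory elevation.

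The causality scale makes the distinction matter. The vector is given once (Section 6.6), so re-challenge cannot occur. Improvement on stopping could be seen only if the infusion of about 60 minutes (Section 4.1.7.2) were interrupted. Taken literally, the Related category is therefore hard to reach for a death that follows a single infusion, and such a death could well be classed as Possibly.

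At stake is whether further dosing stops automatically, with DMC and regulator involvement, or only after someone decides that the event merits it. The rule still has work to do: the schema in Section 1.2 provides for further participants to be dosed at 8-week intervals.

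**Working it through.** No plan figure needs reproducing and no power or error-rate calculation applies. The check is a count of the triggers in Section 4.3.1, followed by tracing where a possibly related death would land.

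**Step 1. Count the triggers.** The thrombosis bullet has two limbs, so seven bullets give eight limbs.

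| Limb | Causality condition? | Expressly covers possibly related? |
|---|---|---|
| 1. Death | Yes | **No** |
| 2. Grade III-IV toxicity, transaminases excluded | Yes | Yes |
| 3. Grade III-IV transaminases not improving within four weeks on immunosuppression | Yes | Yes |
| 4. Grade IV transaminases | Yes | Yes |
| 5a. Thrombotic event with FIX:C >150% | Yes | Yes |
| 5b. FIX activity >150% for more than 6 weeks | No | Not applicable |
| 6. Catch-all for medically important events | No | Not applicable |
| 7. Malignancy | Yes | Yes |

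Conditioned limbs: 8 − 2 = 6. Covering possibly related events: 5 (limbs 2, 3, 4, 5a and 7). Not doing so: 6 − 5 = 1, which is death.

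**Step 2. Trace a possibly related death through the other limbs.**

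- *Limb 2.* Its examples are illustrative, and only transaminases are excluded. Appendix 8 puts many routes to death at Grade 3 or 4: anaphylaxis, acute myocardial infarction, coma or seizures, dyspnea at rest, assisted ventilation, hypertensive crisis, and bilirubin above 3 times baseline. A death that passes through one of these triggers suspension expressly, at the possibly related level.
- *Limbs 3, 4 and 7.* These cover the hepatic transaminase and malignancy routes, also at the possibly related level.
- *Limb 5a.* This needs FIX:C above 150%. A thrombosis at or below that level falls outside it, although some cases (myocardial infarction, for instance) come back in through limb 2.
- *Limb 6.* This has no causality condition and sits under the mandatory opening sentence, so it would probably take most of the rest. It does require a judgment that the event merits further evaluation, and the section does not say who makes that judgment.

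**Step 3. Identify the residual.** The Appendix 8 grades stop at 4. Death is a category on the separate intensity scale in Section 10.3.3, but the Grade III-IV bullet does not refer to that scale. The cases left to limb 6 alone are a possibly related death with no preceding gradable Grade III-IV toxicity, mainly sudden or unwitnessed, and a fatal thrombosis at FIX:C of 150% or less that no Appendix 8 item captures.

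**Step 4. Check whether another passage widens the death bullet.**

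- Section 10.3.3 treats unknown causality as related, but for reporting purposes.
- SAP 9.1.2 and 9.1.6 pool Possible with Related, but for summary tables.
- Neither provision governs enrollment.

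**The case against.** The strongest reply is that the wording difference has almost no consequence, and much of that reply stands.

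- The Grade III-IV toxicity bullet already works at the possibly related level and would catch most fatal toxicities on the way to death. This stands, and it is why the residual is narrow.
- The judgment under the catch-all is close to automatic for a death. Section 8.3.3 requires a summary of available autopsy findings and Section 10.3.3 requires any post-mortem findings, so it is hard to argue that a possibly related death does not merit evaluation. This largely stands. The step is still one that the other causality-conditioned triggers do not need for a possibly related event.
- Drug-related need not mean the category Related. No passage equates the two, and the malignancy bullet uses probably and definitely, which are not on the four-category scale. Drug-related is also the primary-endpoint term, and the SAP pools Possible into Related when tabulating. The causality definitions are to be considered alongside clinical judgment. All of this makes a broader reading possible. It is not stated for this rule, and the neighbouring bullets point the other way.
- Other safeguards operate regardless: 24-hour SAE reporting (Section 8.3.1.1), regular DMC safety review (Section 10.1.5.1), and the sponsor's right to terminate at any time (Section 4.3.1). These make an overlooked death unlikely, but none of them mandates suspension.

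A reader might also infer something stronger: that a death classed as Possibly could not suspend enrollment, or would usually escape the rule. The documents do not support this, because the toxicity, malignancy and catch-all bullets would each suspend enrollment for such a death where they apply.

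**Conclusion.** The point holds as a drafting inconsistency in a safety rule, of low severity. Death is the one trigger of six conditioned on causality that does not expressly include possibly related events. The effect is confined to the residual identified in the working. In those cases enrollment would probably still be suspended, but through a judgment and not through an express rule.

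This rests on two assumptions: that a site may read drug-related as narrower than possibly drug-related, as the list itself suggests, and that the causality definitions are applied more or less literally. If the sponsor already intends the broader reading, nothing changes in practice and the edit only records that intent. The documents give no basis for putting a frequency on the residual case.

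SAE reporting is not affected, because an adverse event that results in death is already an SAE under Section 10.3.2. The SAP tables are not affected either.

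**What to change.** In Protocol Section 4.3.1, insert *or possibly drug-related* after drug-related in the death bullet. Make the same insertion in the parallel list in Section 10.3.2, for consistency only.

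The change to the rule is three words and can go into the next amendment. The SAP, the CRF and the causality scale stay as they are. The downside is a slightly higher chance of a temporary enrollment pause, lasting until the DMC review and regulator discussion are complete, after an event for which review before further dosing is easy to justify.

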#### **4.4. End of Study Definition**

A participant is considered to have completed the study if he has completed all phases of the study including the last scheduled procedure shown in the Schedule of Activities.

The end of the study is defined as the date of the last scheduled procedure shown in the Schedule of Activities for the last participant in the trial globally.

If a decision is made to terminate the study, the Investigators will be notified. No additional participants will be enrolled or dosed and the appropriate end-of-study assessments will be performed for all participants enrolled in the study at that time.

At the time of last subject last visit (LSLV), final assessment results and laboratory tests are generally not available, thereby necessitating the need for follow-up action. Sponsor studies involve specialized tests, which have to be sent to specialized centers; these data then have to be reconciled with the rest of the data. Thus, clinical sites are still active post-LSLV and may only be closed following database lock, when all required participant information has been confirmed as both received and clean, including follow-up information for any SAEs/reactions.

#### **4.5. Extension Study (C0371003)**

Participants who complete study assessments at the defined end of study will be encouraged to enroll in C0371003 evaluating the long-term safety, durability, and efficacy of PF-06838435. A 5-year long-term follow-up (LTFU) is planned based on the November 2006 FDA Guidance entitled Gene Therapy Clinical Trials – Observing Participants for Delayed Adverse Events. The Investigator should discuss the extension plan with the participants prior to enrolling them in this study and again at the End-of-Study (Week 52) visit. Any AEs, safety events or unscheduled visits between Week 52 (or End-of-Study) of this study and the first study visit of the extension study will be captured in the source data for the subject and entered into the extension study database after the subject has agreed and completed the informed consent process.

### **5. STUDY POPULATION**

Prospective approval of protocol deviations to recruitment and enrollment criteria, also known as protocol waivers or exemptions, is not permitted.

#### **5.1. Inclusion Criteria**

Participants are eligible to be included in the study only if all of the following criteria apply:

##### **Age**

1. Participant must be male and  $\geq 18$  years of age inclusive, at the time of signing the informed consent.

**Type of Participant and Disease Characteristics**

2. Have hemophilia B with  $\leq 2$  IU/dL ( $\leq 2\%$ ) endogenous FIX activity levels as documented from a certified clinical laboratory at the time of screening. If the screening result is  $> 2\%$  due to insufficient washout from the FIX product, then the severity of hemophilia B may be confirmed by documented historical evidence from a certified clinical laboratory demonstrating  $\leq 2\%$  FIX coagulant activity (FIX:C) or from a documented genotype known to produce clinically severe phenotype of hemophilia B;
3. Have had  $\geq 50$  prior exposure days (EDs) to any recombinant and/or plasma-derived FIX protein products based on historical data from participant's records/history;
4. a) Prophylaxis participants: Have had bleeding events and/or infusion with FIX products during the last 12 weeks, as documented in the participants' medical records; or
  1. b) On-demand participants: Have had  $\geq 4$  bleeding events in the last 52 weeks and/ or chronic hemophilic arthropathy (pain joint destruction and loss of range of motion) in one or more joints;
5. Have no history of hypersensitivity or anaphylaxis associated with any FIX or IV immunoglobulin administration;
6. Have no measurable FIX inhibitor as assessed by the central laboratory; or documented no prior history of FIX inhibitor after 50 EDs (family history of inhibitors will not exclude the participant) and no clinical signs or symptoms of decreased response to FIX administration;
7. Have acceptable laboratory values sampled at screening and reviewed prior to Day 0:
  - Hemoglobin  $\geq 11$  g/dL;
  - Platelets  $\geq 100,000$  cells/ $\mu$ L;
  - AST, ALT, alkaline phosphatase  $\leq 2x$  upper limit of normal (ULN);
  - Bilirubin  $\leq 3x$  ULN (Bilirubin levels above the laboratory's normal range are acceptable in individuals with a documented history or laboratory evidence of Gilbert's Disease);
  - Creatinine  $\leq 2.0$  mg/dL.

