**3. OBJECTIVES, ESTIMANDS AND ENDPOINTS**

Objectives	Endpoints
Primary	

 
The primary objective is to evaluate the safety and tolerability of a single IV infusion of PF-06838435 in hemophilia B participants ≥18 years of age with ≤2 IU/dL [≤2 %] endogenous factor IX [FIX].
 
	
Clinically significant changes from baseline in the following:
 
 
Physical examination
 
Vital signs
 
Laboratory values
 
Incidence of drug-related adverse events (including inhibitor development)
 
FIX incremental recovery (time at maximum activity [Tmax] and percent recovery for FIX activity)
 
Immune response against AAV capsid protein
 
Immune response against hFIX transgene
 
 
For those individuals who develop hepatic transaminases (ALT and/or AST) elevation of approximately 1.5-fold or successively increasing during follow-up above baseline (or vector-derived FIX:C activity levels decline without evidence of FIX inhibitor, accompanied by rising IFN ELISPOTs on PBMCs) after PF-06838435 infusion, treatment with corticosteroids will be instituted. Alternative immunosuppressive

	
therapies will be considered if the initial corticosteroid treatments are not successful.
 
For any individual who reaches >150% vector-derived FIX:C activity levels after the infusion of PF-06838435, laboratory parameters of thrombotic potential will be assessed.

Secondary	

• The secondary objective is to characterize the kinetics of PF-06838435.

	

• Vector-derived FIX:C activity levels:

• Peak

• Steady-state

• FIX antigen levels

CCI
 	

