#### **4.1.7.1. Screening Period**

Potential participants will undergo the screening assessments described in the Schedule of Activities up to 6 ( $\pm 2$ ) weeks prior to the infusion of PF-06838435 once the consent process is completed at the vector-administration center. If the screening result of FIX:C activity level is  $>2\%$  due to recent infusion of factor IX protein product, then the severity of hemophilia B may be confirmed by documented historical evidence from a certified laboratory demonstrating the FIX:C activity level  $\leq 2\%$  or from a documented genotype known to produce a clinically severe phenotype of hemophilia B. If FIX:C activity is not  $\leq 2\%$  at screening or documented historical evidence is not available and genotype are not known, sample(s) will be drawn for analysis at Screening. Genotype is not a criterion for inclusion or exclusion. However, a documented genotype known to produce a clinically severe phenotype of hemophilia B is required if the participant is otherwise unable to demonstrate severity. Once the eligibility is verified, participants are required to undergo a washout of FIX protein products for at least 96 hours (4 days) prior to the Dosing Day (Day 0) to establish baseline value of FIX:C and FIX inhibitor. The screening period may be extended up to 2 weeks for participants who have a bleeding event requiring FIX protein product infusion within 96 hours prior to Day 0 (Dosing Day). If screening is prolonged greater than 8 weeks, then the FIX inhibitor, anti-AAV-Spark100 capsid antibody, biochemistry, hematology, vital signs, and physical examination screening assessments must be repeated to ensure continued eligibility. The reason for prolongation of screening should be clearly documented.

Screening assessments would also be done to verify participant eligibility are described in [Section 8.10.1](#).

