**Table 3. Protocol-Required Laboratory Assessments**

Assessment	Description
Hematology (CL)	
 
• WBC count with Differential: 
 
○ Neutrophils
 
○ Lymphocytes
 
○ Monocytes
 
○ Eosinophils
 
○ Basophils
 
 
 
• RBC count
 
• Hemoglobin
 
• Hematocrit
 
• Platelet count
 

Clinical Chemistry (CL)	
 
• Sodium
 
• Potassium
 
• Chloride
 
• Bicarbonate
 
• Glucose
 
• Phosphate
 
• Serum creatinine
 
• BUN
 

Lipid Panel (CL)	
 
• LDL
 
• VLDL
 
• HDL
 
• Triglycerides
 
• Total Cholesterol
 

ABO (LL)	
 
• ABO group
 

Urinalysis (CL)	
 
• pH
 
• Specific Gravity
 
• Protein
 
• Blood
 
• Ketones
 
• Glucose
 

Liver Function Tests (LL and CL)	
 
• Albumin,
 
• Total bilirubin
 
• Direct bilirubin
 
• Indirect bilirubin
 
• ALP
 
• AST
 
• ALT
 
• Total protein
 
• GGT
 
• LDH
 

Liver Fibrosis (CL)	
 
• FibroTest/Fibrosure (if applicable)
 

Coagulation (LL, CL as noted)	
 
• FIX activity, aPTT (LL and CL)
 
• FIX antigen, INR, TAT, CCI (CL)
 
• ROTEM and/or TEG (LL where available)
 
• FIX inhibitor (Nijmegen Bethesda), (LL screening visit only, CL screening and all other visits)
 

AAV Neutralizing Antibody (CL)	
 
• PF-06838435 Neutralizing Antibody
 

Immunology (CL)	
 
• ELISPOT IFN-γ with PBMCs to assess cellular immune responses to AAV capsid and to FIX
 

CCI	

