9.2.3. Bethesda Assay for Inhibitor Assessment

FIX Inhibitor results by Bethesda Assay from the central and local lab will be presented in a data listing.

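### Inclusion item 6 lets a clean history stand in for a negative central-laboratory FIX inhibitor result, in conflict with Protocol 4.1.7.1, which repeats that test to confirm eligibility

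*Protocol*

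**What the plan says.** Protocol 5.1, item 6, has three clauses. The first two are "Have no measurable FIX inhibitor as assessed by the central laboratory; or documented no prior history of FIX inhibitor after 50 EDs". The third is "and no clinical signs or symptoms of decreased response to FIX administration". Section 5 allows no waivers, so the written criteria govern.

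The exclusion criteria in Protocol 5.2 do not mention FIX inhibitors. Only item 8, the general discretion of the investigator or sponsor, could catch an inhibitor-positive participant.

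The test is run in everyone. Table 3 in Appendix 2 lists "FIX inhibitor (Nijmegen Bethesda), (LL screening visit only, CL screening and all other visits", and the Schedule of Activities places the Bethesda assay at screening and before dosing on Day 0. Protocol 4.1.7.1 says the washout before Day 0 serves "to establish baseline value of FIX:C and FIX inhibitor". If screening runs beyond 8 weeks, the same section names the inhibitor test among those whose "screening assessments must be repeated to ensure continued eligibility".

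Inhibitors matter later in the trial. The primary endpoint list in Protocol 3 includes "Incidence of drug-related adverse events (including inhibitor development". The suspension rules in Protocol 4.3.1 include "Any participant develops drug-related or possibly drug-related Grade III-IV toxicity such as FIX inhibitor". On analysis, SAP 9.2.3 says only that "FIX Inhibitor results by Bethesda Assay from the central and local lab will be presented in a data listing".

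**The concern.** An eligibility rule meant to keep inhibitors out does not do so as written. The central test is performed, but for a man with a clean history and no signs a positive result does not make him ineligible. That conflicts with Protocol 4.1.7.1, which repeats the test because its result is supposed to bear on eligibility.

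Three things are at stake if such a man is dosed. First, a titre that persists or rises after infusion has to be attributed either to the vector or to his prior state, and the SAP gives no rule for participants who are positive at baseline. Second, Protocol 2.2.2 describes inhibitors as neutralising FIX activity. His FIX incremental recovery, another item on the primary endpoint list, could be low for reasons unrelated to the vector. Third, his FIX:C could also be lowered, and FIX:C decides escalation and expansion under Protocol 4.1.3.1. When expansion needs 3 of 5, or 6 of 10, participants above 5%, one such value can decide the outcome if the count is at the margin.

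**Working it through.** **Logic of item 6.** Let A = no inhibitor on the central test, B = no prior history after 50 exposure days, C = no signs of decreased response. The punctuation allows two groupings. The last column shows what a blanket change to "and" would do.

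| A | B | C | A or (B and C) | (A or B) and C | A and B and C |
|---|---|---|---|---|---|
| no | no | no | fails | fails | fails |
| no | no | yes | fails | fails | fails |
| no | yes | no | fails | fails | fails |
| **no** | **yes** | **yes** | **meets** | **meets** | **fails** |
| yes | no | no | meets | fails | fails |
| yes | no | yes | meets | meets | fails |
| yes | yes | no | meets | fails | fails |
| yes | yes | yes | meets | meets | meets |

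The bold row is the participant in question. He qualifies under both groupings, so the gap does not depend on how the sentence is read. The sixth row, a past inhibitor with a negative current test and no signs, qualifies today under both groupings and would be excluded if every clause became mandatory. The fifth row, a past inhibitor with signs of decreased response and a negative test, qualifies under the first grouping only.

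**Side by side with Protocol 4.1.7.1.** For a man with B and C true, item 6 is met whatever A is. Repeating the test therefore cannot change his status under item 6, yet the repeat is required for exactly that purpose.

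**Scale, if one such participant were counted as a case.** SAP 9.1.2 bases percentages on all dosed participants in the dose group, so the shift is 1/n. Protocol 4.1.3.1 gives dose levels of 5, 10 or 20:
- n = 20: 1/20 = 5.0 points
- n = 10: 1/10 = 10.0 points
- n = 5: 1/5 = 20.0 points

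**Chance that at least one arises.** The documents give no prevalence p at screening, so p is an assumption. With about 20 dosed (Protocol 9.2), the chance is 1 − (1 − p)^20:
- p = 0.5%: 1 − 0.995^20 = 9.5%
- p = 1%: 1 − 0.99^20 = 18.2%
- p = 3%: 1 − 0.97^20 = 45.6%
- p = 5%: 1 − 0.95^20 = 64.2%

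The last two values borrow the 3-5% in Protocol 2.2.2. That figure is the share of patients who develop an inhibitor following exposure. It is not the prevalence of a newly found inhibitor in adults with a clean history and no signs, so it serves only as an upper range. There is no sample size or power figure to reproduce, since the trial tests no hypothesis.

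**The case against.** The strongest reply is that the sentence can be rescued. Item 3 requires at least 50 exposure days, so an inhibitor found at screening is itself one found after 50 exposure days, and an investigator could say the history clause then fails. The text does not say this, and the word "prior" points the other way. On that reading B could be true only when A is true, and the history alternative would do no work at all. Exclusion item 8 could also catch such a man, but it is discretionary.

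A reader might infer that the inhibitor endpoint is undermined, or that pre-existing inhibitors would falsely suspend enrolment. The documents do not support that:
- Titres at screening and Day 0 give a baseline, and every result is listed.
- Protocol 8.3.1 sends conditions arising between consent and infusion to medical history, and SAP 9.1 counts only events starting on or after infusion.
- The suspension rule concerns an inhibitor that develops and is at least possibly drug-related. In Appendix 8, Grade 3-4 starts at 5.0 B.U.; 0.5-4.9 B.U. is Grade 1-2. A false suspension would need a high titre in a man without reduced response, or a low titre that rises after dosing, and the latter is a legitimate safety signal.

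A reader might also apply the 3-5% as the chance that a screened man is positive. It is not that figure. These limits reduce the consequence; they do not close the gap in item 6.

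**Conclusion.** The point holds as a defect in the eligibility rule with a limited effect on the endpoint. Item 6 admits a participant with a newly measurable inhibitor under either grouping, no other criterion names inhibitors, and Protocol 4.1.7.1 treats the test as bearing on eligibility. The consequence is an avoidable attribution problem, with possible lowering of FIX recovery and FIX:C by an amount the documents do not allow one to estimate.

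The 5, 10 and 20 point shifts are conditional on a pre-existing inhibitor actually being counted as a new case, which the baseline titres and event-dating rules make unlikely. The 9.5% to 64.2% range rests wholly on assumed prevalence and describes a man presenting with an inhibitor, not a miscount. Whether anyone entered this way cannot be known from the documents. The change is worth making because it is cheap and removes the conflict between the two sections.

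**What to change.** Reconcile Protocol 5.1, item 6, with 4.1.7.1. Reword item 6 so that a negative central-laboratory inhibitor result at screening is a requirement in its own right and not an alternative to history. Then state in a separate sentence whether the history and clinical-signs clauses are also required. Simply replacing the "or" by "and" would settle that second question silently, because it would also exclude men with a past inhibitor and a negative current test.

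The cost is a short text amendment. The test is already run at screening, so no procedure is added and no sample size or power figure changes. The downside is a possible small loss of eligible participants: those with a positive result who would now qualify on history and absence of signs, plus, if the other clauses are made mandatory, those with a past inhibitor or with signs of decreased response.
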